#### Please also refer to Appendix 5.

Management and safety of individual patients is under the clinical judgement of the investigator who may choose to withhold study treatment even if hold criteria are not formally met as per protocol.

All treatment delays will be reported in the eCRF. A treatment delay >4 days for cemiplimab should be justified. Treatment may be delayed no more than 12 weeks to allow recovery from acute toxicity. After cycle 5 patients may have up to 3 weeks break in their treatment for reasons other than toxicity at the discretion of the PI (maximum of two breaks in the course of a patient's treatment). The reason for the break needs to be provided. Please also see Appendix 6 for contingency measures during extenuating circumstances. In case of treatment delay of greater than 12 weeks, the patient should discontinue the study treatment, unless there is strong evidence for tumour response justifying continuation. The investigator must discuss the rationale with the Chief Investigator before a decision is taken.

Subjects may resume treatment with cemiplimab when drug-related AEs resolve to grade 1 or baseline value and steroid use is reduced to ≤ 10mg/day prednisolone or equivalent.

#### **Exceptions:**

- Subjects may resume treatment in the presence of grade 2 fatigue.
- Drug-related pulmonary toxicity, diarrhoea or colitis must have resolved to baseline levels before treatment is resumed.
- Drug-related endocrinopathies adequately controlled with only physiologic hormone replacement may resume treatment

#### Please also refer to Appendix 5.

#### 7.5.3 Infusion-related reactions

Acute infusion reactions are defined as any AE that occurs during the infusion or within 2 hours after the infusion is completed. Emergency equipment and medication for the treatment of infusion reactions must be available for immediate use. All infusion reactions must be reported as AEs and graded. In the event of an infusion reaction of grade 3 or greater severity during or directly following cemiplimab infusion, dosing should be stopped and the patient must be permanently discontinued from cemiplimab treatment.

To assist investigators in identifying cemiplimab-related infusion reactions, the following case definition is provided.

- Typical symptoms may include fever, chills, rigors, skin flushing, dyspnea, back pain, abdominal pain, and nausea
- Infusion reactions usually occur either during the infusion or within 2 hours after the infusion is completed
- Vital signs may be notable for hypotension and/or tachycardia

Case report forms will capture start and stop time of the event, signs and symptoms, and management interventions (medications, interruption of infusion, rate reduction).

The infusion should be interrupted if any of the following are observed:

- Cough
- Rigors/chill
- Rash
- Pruritis
- Urticaria (hives, welts, wheals)
- Diaphoresis (sweating)
- Hypotension
- Dyspnoea (shortness of breath)
- Vomiting
- Flushing

If investigators feel there is a medical need for treatment or discontinuation of the infusion other than described above, they should use clinical judgment to provide the appropriate response according to typical clinical practice

After symptomatic treatment the infusion may be restarted at 50% of the original rate. For patients who experience infusion-related hypersensitivity reactions that are less than grade 3 and who plan to continue treatment, premedication will be required for re-treatment

**For grade 1 symptoms** (mild reaction; infusion interruption not indicated; intervention not indicated), the following prophylactic medications are recommended for future infusions: diphenhydramine 50 mg (or equivalent) and/or acetaminophen/paracetamol 325 mg to 1000 mg at least 30 minutes prior to subsequent cemiplimab infusions.

For grade 2 symptoms (moderate reaction that requires therapy or infusion interruption, but for which symptoms resolve promptly with appropriate treatment such as antihistamines, nonsteroidal anti-inflammatory drugs, narcotics, corticosteroids, and/or IV fluids; prophylactic medications indicated 24 hours), the following prophylactic medications are recommended for future infusions: diphenhydramine 50 mg (or equivalent) and/or acetaminophen/paracetamol 325 mg

to 1000 mg at least 30 minutes prior to subsequent cemiplimab infusions. If necessary, corticosteroids (up to 25 mg of hydrocortisone or equivalent) may be used.

#### **Termination of infusion**

In the event of an infusion reaction grade ≥3 during or directly after cemiplimab infusion, treatment should be discontinued permanently

If any of the following AEs occur the infusion should be terminated and NOT restarted

- Anaphylaxis
- Laryngeal/pharyngeal oedema
- Severe bronchospasm
- Chest pain
- Seizure
- Severe hypotension
- Other neurological symptoms (confusion, loss of consciousness, paresthesis, paralysis etc.)
- Any other symptom or sign that, in the opinion of the investigator, warrants discontinuation of the infusion

#### 7.5.4 Treatment Discontinuation

- Any grade 4 drug-related AE or laboratory abnormality.
  - Exceptions for immune related (irAEs); grade 3 or recurrent grade 2 pneumonitis, grade 3 hepatitis, nephritis, neurological toxicity, myocarditis or pericarditis, any recurrent grade 3 irAE.
- Any infusion reaction grade ≥3 during or directly after cemiplimab infusion.
- Any dosing interruption to cemiplimab lasting longer than 12 weeks
- Any AE, laboratory abnormality or intercurrent illness which in the judgment of the investigator presents a substantial risk to the subject with continuing drug dosing.
- Patients diagnosed with progressive disease, unless continuation of cemiplimab
  is deemed to be of clinical benefit e.g. it is within the first 12 weeks of treatment
  and thought to be pseudo-progression, in which case it should be discussed with
  the Chief Investigator or nominated representative (if treatment continues trial
  activity also needs to be performed as per the visit schedule).

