#### 9.1 Permanent treatment discontinuation from the IMP

Permanent treatment discontinuation is any treatment discontinuation associated with the definitive decision from the investigator or the patient not to re-expose the patient to the IMP at any time.

If a patient shows one of the following reasons, the study treatment must be discontinued:

- Progression of basal cell carcinoma as per clinical response criteria/RECIST 1.1/composite response criteria (unless continuation of cemiplimab is deemed to be of clinical benefit e.g. it is within the first 12 weeks of treatment (scan 1) and thought to be pseudo-progression, in which case it should be discussed with the CI or nominated representative).
- Unacceptable toxicity or adverse event requiring discontinuation of treatment
- Patient requests to stop treatment including if they change their mind about wanting curative surgery e.g. if the surgery is curative but potentially disfiguring
- Patient shows non-compliance (including persistent patient attendance failure).

The patients may withdraw from treatment with IMP at any time and irrespective of the reason, or this may be the investigator's decision. The reason for treatment discontinuation will be documented as far as possible on the appropriate eCRF.

Further medical or surgical treatment following trial immunotherapy is at the discretion of the treating clinician in consultation with the patient.

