# APPENDIX 5: GUIDELINES FOR MANAGEMENT OF SELECTED IMMUNE-RELATED ADVERSE EVENTS

Pneumonitis Grade	Study treatment Management	Action & Supportive Care Guidelines	Diagnostic Considerations
Grade 1	Consider withholding study treatment.	
 
Monitor symptoms every 2-3 days
 
Consider consultation with pulmonologist
 
Consider chest imaging (CT or X-ray) followed by serial imaging at least every 3 weeks to monitor resolution or progression
 
May resume study treatment upon improvement or resolution. If no improvement treat as G2
 
	All attempts should be made to rule out othe causes such as metastatic disease, bacteria or viral infection.
Grade 2	Withhold study treatment.  Permanently discontinue study treatment if patient develops a 2 nd episode of ≥G2 pneumonitis upon rechallenge	
 
Monitor symptoms daily; consider hospitalisation
 
Consider consultation with pulmonologist
 
Consider chest imaging (CT or X-ray) followed by serial imaging at least every 3 weeks to monitor resolution or progression
 
Consider bronchoscopy with bronchoalveolarlavage (BAL) to rule out infection and malignant lung infiltration
 
Consider pulmonary function tests and laboratory work up for infections
 
Treatment with systemic corticosteroids (1-2 mg/kg/day prednisone or equivalent) until resolution to ≤G1 and taper over at least a month
 
If symptoms do not improve within 48-72 hours of corticosteroid treatment treat as G3
 
Consider empiric antibiotics if infection has not yet been fully excluded
 
	

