Grade 3-4	Permanently discontinue study treatment.	
 
Inpatient care
 
Consultation with pulmonologist and infectious disease specialist
 
Consider bronchoscopy with bronchoalveolarlavage (BAL) to rule out infection and malignant lung infiltration
 
Empiric antibiotics if infection has not yet been fully excluded
 
Add prophylactic antibiotics for opportunistic infections
 
Treatment with systemic corticosteroids (2-4 mg/kg/day prednisone or equivalent) until resolution to ≤G1 and taper over at least a month
 
If symptoms do not improve within 48-72 hours of corticosteroid treatment consider additional immunosuppressive treatment i.e. mycophenolate mofetil 1-1.5 g BID, infliximab 5mg/kg IV
 
If symptoms worsen during steroid reduction, initiate a re-tapering of steroids starting at a higher dose of 80 or 100 mg followed by a more prolonged taper
 
	

Kecomme	enaea Aaverse	Event Management for Collitis/Diarrhoea	
Colitis/ Diarrhoea Grade	Study treatment Management	Action & Supportive Care Guidelines	Diagnostic Considerations
Grade 1	No change	
 
Treat symptomatically (loperamide, oral hydration, electrolyte substitution and ADA colitis diet)
 
Consider consultation with gastroenterologist for prolonged symptoms
 
If symptoms are persistent, consider endoscopic evaluation.
 
If persists for >2 weeks treat as G2
 
	All attempts should be made to rule out other causes such as metastatic disease, bacterial or parasitic infection, or viral
Grade 2	Withhold study treatment	
 
Treat symptomatically (loperamide, oral hydration, electrolyte substitution and ADA colitis diet).
 
Consultation with gastroenterologist.
 
Consider colonoscopy ± esophagogastroduodenoscopy (EGD), or endoscopy
 
Consider stool evaluation to rule out infectious aetiology
 
Consider stool inflammatory marker evaluation (i.e. lactoferrin and calprotectin) to differentiate functional vs inflammatory diarrhoea.
 
Consider abdominal and pelvic CT with contrast
 
Treatment with systemic corticosteroids (1-2 mg/kg/day prednisone or equivalent) until resolution to ≤G1 and taper over at least a month
 
	gastroenteritis

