Grade 3	Withhold study treatment  Permanently discontinue study treatment if recurrent G3 colitis is experienced	
 
If no improvement within 2-3 days treat as G3
 
Treat symptomatically (loperamide, oral hydration, electrolyte substitution and ADA colitis diet).
 
Consultation with gastroenterologist.
 
Consider colonoscopy ± esophagogastroduodenoscopy (EGD), or endoscopy
 
Consider stool evaluation to rule out infectious aetiology
 
Consider stool inflammatory marker evaluation (i.e. lactoferrin and calprotectin) to differentiate functional vs inflammatory diarrhoea.
 
Consider abdominal and pelvic CT with contrast
 
Inpatient care for close monitoring and supportive care
 
Treatment with systemic corticosteroids (1-2 mg/kg/day prednisone or equivalent) until resolution to ≤G1 and taper over at least a month
 
If no improvement within 2-3 days treat as G3
 
If no improvement with corticosteroid within 2-3 days, consider additional immunosuppressive treatment i.e. mycophenolate 0.5-1 g BID, infliximab 5mg/kg IV
 
	
Grade 4	Permanently discontinue study treatment	Same as above     Consider lower GI endoscopy if symptoms are refractory despite the treatment or there is a concern of new infections	

Recommen	Recommended Adverse Event Management for Immune-Mediated Hepatitis		
Immune- Mediated Hepatitis Grade*	Study treatment Management	Action & Supportive Care Guidelines	Diagnostic Considerations
Elevated ALT & AST> ULN – 3 x ULN without elevated bilirubin	No change	Monitor liver function tests (LFT) more frequently until resolution to baseline values	All attempts should be made to rule out other causes such as metastatic disease,
Elevated ALT & AST> 3 and≤ 5 x ULN or if total bilirubin >1.5 and ≤ 3 x ULN	Withhold study treatment	
 
Monitor liver function tests (LFT) more frequently until resolution to baseline values
 
Consider appropriate consultation with hepatologist and liver biopsy to establish aetiology of hepatic injury, if necessary
 
Consider inpatient monitoring for patients with ALT/AST>8x ULN and/or elevated bilirubin >3x ULN
 
	progressive liver disease, viral hepatitis, alternative drug toxicity, infectious causes and/or myositis

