		
 
Treatment with systemic corticosteroids (1-2 mg/kg/day prednisone or equivalent) until resolution to ≤G1 and taper over at least 1 month
 
If no improvement within 3 days after initiation of systemic steroids, consider additional immunosuppressive treatment i.e. mycophenolate mofetil 0.5-1 g BID
 
Several courses of steroid tapering may be necessary as symptoms may worsen when the steroid dose is decreased
 
	*Please note that the gradings of immune- mediated hepatitis are not according to CTCAE v5.0
Elevated ALT & AST> 5 x ULN or if total bilirubin > 3 x ULN	Permanently discontinue study treatment	Same as above	

Recomme	ended Adverse	Event Management for Endocrine Events	
Grade 1	No Change	
 
Hypo/hyperthyroid: monitor thyroid function or other hormonal level more frequently (every 3-6 weeks) until resolution to baseline
 
There should be low index of suspicion for immune-related endocrinopathy including checking TSH, T4, cortisol and adrenocorticotropic hormone levels if clinically appropriate
 
	Immune related endocrinopathies can have subtle and wide-ranging presentations. Please refer to expert panel consensus
Grade 2-4	Withhold Study treatment if clinically necessary	
 
Consult with endocrinologist and provide supportive care per institutional guidelines
 
Rule out infection and sepsis with appropriate cultures and imaging
 
Hypo/hyperthyroid:         
 
Replacement of thyroid hormone or thyroid suppression therapy as indicated.
 
Thyroid hormone and/or steroid replacement therapy to manage adrenal insufficiency
 
 
 
	guidance documents for further guidance. All attempts should be made to rule out other causes such as brain metastases, sepsis, and/or infection.

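### Section 7.5.4 and Appendix 5 conflict on grade 4 endocrine events, and the line headed as exceptions to the grade 4 stop is in substance a list of extra stop triggers

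*Protocol*

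**What the plan says.** - Section 7.5.4 lists the reasons for discontinuing cemiplimab. The first is "Any grade 4 drug-related AE or laboratory abnormality". Endocrine events are not carved out.
- A sub-bullet under that rule reads "Exceptions for immune related (irAEs); grade 3 or recurrent grade 2 pneumonitis, grade 3 hepatitis, nephritis, neurological toxicity, myocarditis or pericarditis" and closes with any grade 3 immune-related event that recurs.
- The Appendix 5 endocrine table has a single row for grades 2 to 4. Its only instruction about study drug is "Withhold Study treatment if clinically necessary".
- Section 7.5.2, in its own list of exceptions, lets a patient restart when a drug-related endocrinopathy is controlled by physiologic hormone replacement alone. It sets no upper grade.
- Section 9.1 requires permanent discontinuation for "Unacceptable toxicity or adverse event requiring discontinuation of treatment". It names no grade and points to neither 7.5.4 nor Appendix 5.
- No text ranks section 7.5.4 against Appendix 5.

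**The concern.** There are two faults in one stopping rule.

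First, a grade 4 drug-related endocrine event must end treatment under section 7.5.4. Under Appendix 5 it need only be held if the clinician sees a need, and under section 7.5.2 it may restart once controlled. Two sites in this multi-centre trial could each cite the protocol and act in opposite ways. Following 7.5.4 is the cautious course, so the likely cost is inconsistent stopping, including the loss of treatment for patients whom the endocrine guidance would have kept on drug.

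Second, a line headed as exceptions to a grade 4 stop invites the reading that the listed events are spared. Here the risk runs towards too much exposure, and it is greatest for the events that have no table elsewhere in the protocol to correct the reader.

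**Working it through.** No arithmetic beyond counting applies, so the check sets the texts side by side.

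**1. A grade 4 drug-related endocrine event.**
- Section 7.5.4: discontinue.
- Appendix 5, endocrine row, which names grade 4: hold if clinically necessary.
- Section 7.5.2, exceptions: may restart when controlled on hormone replacement, any grade.

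The first instruction ends treatment and the other two do not.

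**2. Is Appendix 5 only about temporary holds?** No. It orders permanent discontinuation in six places: pneumonitis 2 (a second episode of grade 2 or higher; grade 3-4), colitis/diarrhoea 2 (recurrent grade 3; grade 4), hepatitis 1 and renal 1, so 2 + 2 + 1 + 1 = 6. In pneumonitis and colitis it does so at grade 4. The endocrine table contains no such order (0).

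**3. What the sub-bullet contains.** Taking grade 3 to govern hepatitis and the four events after it:

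| Trigger | Grade | Appendix 5 |
|---|---|---|
| Pneumonitis | 3 | Grade 3-4 row: "Permanently discontinue study treatment" |
| Pneumonitis, recurrent | 2 | Stops at a second "episode of ≥G2 pneumonitis upon rechallenge" |
| Hepatitis | 3 | Stops at "Elevated ALT & AST> 5 x ULN or if total bilirubin > 3 x ULN", on a scale stated not to be CTCAE |
| Nephritis | 3 | Severe renal row stops (creatinine above 3 times baseline), also not CTCAE |
| Neurological toxicity | 3 | No table |
| Myocarditis | 3 | No table |
| Pericarditis | 3 | No table |
| Any irAE, recurrent | 3 | "Permanently discontinue study treatment if recurrent G3 colitis is experienced" (colitis only) |

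That makes eight triggers, none at grade 4. Three have an Appendix 5 stop on a matching grade and two have one on a different scale (3 + 2 = 5). Three have none (5 + 3 = 8).

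**4. Sensitivity to the parsing.** If grade 3 attaches to hepatitis alone, then nephritis, neurological toxicity, myocarditis and pericarditis carry no grade. Four triggers are then explicitly below grade 4 (8 − 4 = 4) and four are ungraded. Still no grade 4 event is named. An exemption reading would also collide with the Appendix 5 renal row, which stops treatment for severe and life-threatening events.

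**5. Response-rate analysis.** Under section 6.5.1, patients who stop for reasons other than progression keep 12-weekly assessment until progression, for at most 12 months. Outcome data are therefore still collected. What remains is any effect of reduced exposure in patients who have such an event before the 6-month assessment.

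**The case against.** **Section 7.5.4 plainly governs stopping.** Appendix 5 is titled as guidelines and its tables as recommended management. Both pointers to it sit in section 7.5.2, on dose delay, and 7.5.4 has none. Its endocrine row does not say that treatment may continue after grade 4, so the 7.5.4 stop could simply apply on top. A site that carried on without a hold would also breach 7.5.2, which delays dosing for non-skin drug-related events of grade 2 or more, fatigue excepted. This has weight. A reader might infer that the endocrine row deliberately permits continuation at grade 4; that is an argument from silence, and the document does not establish it. What stands is that the row names grade 4 with a weaker instruction, that the restart permission is itself in the main text, and that no order of precedence is written.

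**The heading on the sub-bullet can be understood.** It sits under treatment discontinuation and makes sense as exceptions to the grade 4 threshold, that is, events that stop treatment sooner. Section 7.5.2 uses the word both ways: it exempts leukopenia and lymphopenia from delay, but gives ALT and bilirubin a lower threshold. The exemption reading is strained. A reader might infer that the protocol allows a restart after grade 3 myocarditis through the general resumption rule in 7.5.2. It does not say so: that would need the strained reading and would pass over the 7.5.4 bullet on investigator-judged substantial risk. The Investigator Brochure, to which section 7.5 refers for the full list of risks, may also cover these events, but it is not at hand. The wording is still wrong for a rule that sites apply directly.

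**The skin table.** A reader might see a further conflict because the severe skin row only withholds. That table is limited to maculopapular rash and suspected SJS/TEN, and not repeating the grade 4 stop does not contradict it.

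**Conclusion.** Two defects hold. Grade 4 drug-related endocrine events receive incompatible instructions with no stated order of precedence. The sub-bullet under the grade 4 rule is mislabelled: in substance it adds stop triggers below grade 4, which Appendix 5 confirms for pneumonitis, hepatitis, renal events and recurrent grade 3 colitis. For neurological toxicity, myocarditis and pericarditis that meaning is inferred from where the line sits.

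The count of no grade 4 triggers among eight assumes that grade 3 carries across the list. The mislabelling does not depend on that assumption.

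The consequence is for patient safety and uniform stopping across sites. The sample size, the two-stage decision rule and the error rates are untouched, and the effect on the response-rate analysis is small. How many patients would be affected cannot be estimated, because the protocol gives no event rates.

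**What to change.** 1. Replace the sub-bullet in section 7.5.4 with wording such as: *In addition, stop permanently for these irAEs: pneumonitis of grade 3, or of grade 2 if recurrent; hepatitis, nephritis, neurological toxicity, myocarditis or pericarditis of grade 3; any grade 3 irAE that recurs.* The sponsor should confirm that grade 3 is meant for each event named.
2. Subject to clinical confirmation, choose one course for grade 4 endocrinopathies. Either exempt in 7.5.4 those controlled on physiologic hormone replacement, which agrees with 7.5.2 and Appendix 5, or add the grade 4 stop to the Appendix 5 endocrine row.
3. State that, apart from any such exemption, the stricter of 7.5.4 and Appendix 5 decides permanent discontinuation. Simply giving 7.5.4 precedence would be unsafe, because it could displace the hepatitis and renal stops that Appendix 5 sets on laboratory thresholds outside CTCAE.

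The cost is amendment wording and a note to sites, with no extra visits, procedures or patients.

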# 7.5.2 Cemiplimab dose delay

Cemiplimab should be delayed for the following:

- Any grade 3 or grade 2 lasting longer than a week, skin drug related AE, or suspected Stevens-Johnson syndrome or toxic epidermal necrolysis
- Any grade 3 drug related laboratory abnormality including Hypothyroidism/Hyperthyroidism and Type 1 diabetes related hyperglycaemia; exception for leukopenia and lymphopenia, ALT and bilirubin.
  - ALT/bilirubin delay dosing for drug-related grade ≥2 toxicity
- Any grade ≥2 non-skin, drug related AE except fatigue.
- Any AE, laboratory abnormality or intercurrent illness which in the judgment of the investigator warrants delaying the dose of study medication.

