# Recommended Adverse Event Management for Immune-related Skin Toxicities

Immune-related skin toxicities include maculopapular rash, dermatitis rash generalised, dermatitis bullous, drug eruption, erythema, rash erythematous, rash macular, rash pruritic and skin reaction. Guidance here is provided for maculopapular rash. For other immune-related skin toxicities, see the cemiplimab IB.

Mild (grade 1) Rash covering <10% BSA with or without symptoms	No change	Treatment with mild to moderate potency topical steroids Treatment with oral antihistamine	All attempts should be made to rule out other causes such as metastatic disease,
Moderate (grade 2) Rash covering 10-30% BSA with or without symptoms, limiting instrumental ADL	Consider withholding study treatment. Withhold study treatment if grade 2 lasts longer than 1 week	Consider consultation with dermatologist and skin biopsy for diagnosis of bullous dermatitis.  Treatment with medium to high potency topical steroids AND/OR with systemic corticosteroids (1-2 mg/kg/day prednisone or equivalent) until resolution to ≤G1 and taper over at least 1 month  Treatment with oral antihistamine	infection, contact dermatitis, effect of another drug or skin condition linked to another systemic disease.
Severe (grade 3 and above) Rash covering >30% BSA with moderate or severe symptoms, limiting self-care ADL OR suspected Stevens-Jonson syndrome (SJS) or toxic epidermal necrolysis (TEN).	Withhold study treatment	Consider consultation with dermatologist and skin biopsy Treatment with high potency topical steroids AND with systemic corticosteroids (1-2 mg/kg/day prednisone or equivalent) until resolution to ≤G1 and taper over at least 1 month Treatment with oral antihistamine	

Recommen	ded Adverse	Event Management for Renal Events	
Mild Elevated creatinine > 1.5-2 x above baseline; increase of ≥0.3 mg/dL	Consider withholding study treatment	
 
Provide symptomatic treatment
 
Monitor creatinine weekly; when it returns to baseline, resume routine creatinine monitoring per protocol
 
	All attempts should be made to rule out other causes such as obstructive uropathy, progression of

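### Appendix 5 is softer than section 7.5 on dosing for grade 3 and 4 endocrine events and for grade 4 maculopapular rash, and no text says which governs

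*Protocol*

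**What the plan says.** Protocol section 7.5.2 lists the events for which cemiplimab should be delayed. One entry is "Any grade 3 drug related laboratory abnormality including Hypothyroidism/Hyperthyroidism and Type 1 diabetes related hyperglycaemia". Another covers non-skin drug-related adverse events of grade 2 or higher, fatigue excepted. For skin, the delay applies at grade 3, at grade 2 persisting beyond a week, and for suspected Stevens-Johnson syndrome (SJS) or toxic epidermal necrolysis (TEN) with no grade given.

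Section 7.5.4, on treatment discontinuation, begins with "Any grade 4 drug-related AE or laboratory abnormality".

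Appendix 5 then gives management tables by event type. The endocrine table has one row for grades 2 to 4, and its treatment instruction is "Withhold Study treatment if clinically necessary". The skin table's top row starts "Severe (grade 3 and above) Rash covering >30% BSA with moderate or severe symptoms, limiting self-care ADL", also names suspected SJS or TEN, and says to withhold. The text above that table limits its guidance to maculopapular rash and sends other skin toxicities to the Investigator's Brochure.

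The only link between the two texts is a request in section 7.5.2, made twice, to consult Appendix 5 as well.

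**The concern.** A drug-related grade 4 endocrine event meets a discontinuation criterion in section 7.5.4. In Appendix 5 the same event does not require even a hold unless someone judges one to be clinically necessary. At grade 3 the contrast is between a delay with no condition attached and a discretionary hold.

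Section 7.5 itself names endocrinopathies and skin reactions among the most common immune-related events with cemiplimab. In a multi-centre trial, a site working from the Appendix 5 table could keep dosing through a grade 3 endocrine event. It could also hold and later re-dose after a grade 4 event that section 7.5.4 lists for discontinuation. While both texts stand, it is unclear whether such a site has deviated from the protocol. What is at stake is patient safety and consistent handling of deviations, not the efficacy analysis.

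**Working it through.** The protocol states no figure on this point, so the check is a comparison of rules for drug-related events.

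| Event | Section 7.5 | Appendix 5 | Result |
|---|---|---|---|
| Endocrine, grade 3 | Delay (7.5.2) | Withhold only if clinically necessary | Appendix softer |
| Endocrine, grade 4 | Discontinue (7.5.4) | Withhold only if clinically necessary | Appendix softer |
| Maculopapular rash, grade 3 | Delay (7.5.2) | Withhold | Agree |
| Maculopapular rash, grade 4 | Discontinue (7.5.4) | Withhold | Appendix softer |
| Suspected SJS or TEN | Delay, no grade limit (7.5.2); discontinue if grade 4 (7.5.4) | Withhold | 7.5.2 and Appendix 5 agree; at grade 4 the tension is inside section 7.5 |

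**Is withhold just another word for stop?** No. Appendix 5 uses "Permanently discontinue study treatment" as a separate instruction. Top-grade entries by table:

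- permanent stop stated: pneumonitis grade 3-4; colitis grade 4; hepatitis with transaminases above 5 x ULN or bilirubin above 3 x ULN; renal severe or life-threatening = 4 tables
- permanent stop not stated: endocrine grade 2-4; skin grade 3 and above = 2 tables
- total: 4 + 2 = 6 tables

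**Are the grades on the same scale?** Appendix 5 notes that its hepatitis and renal gradings depart from CTCAE v5.0. The endocrine and skin tables carry no such note, so a change of scale does not explain the difference.

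**Does another clause settle it?**

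- The sub-bullet on immune-related exceptions in 7.5.4 can be read as extra stop triggers or as exemptions from stopping. Neither reading covers a grade 4 endocrine or grade 4 skin event, because neither is listed.
- The investigator-discretion clause in 7.5.2 works one way. It allows a hold when the criteria are not met; it does not allow dosing when they are.
- The line "Drug-related endocrinopathies adequately controlled with only physiologic hormone replacement may resume treatment" governs restart after a delay. It does not waive the grade 3 delay. Because it has no grade limit, it leaves unclear how it sits with the grade 4 stop.
- Appendix 5 is headed as guidelines, but so is section 7.5, so the headings give no order of precedence.

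**Grade 2 endocrine events** are not counted. Section 7.5.2 sets its laboratory entry at grade 3 and its non-skin adverse event entry at grade 2 or higher. Which one catches a grade 2 thyroid result is a question within section 7.5.2.

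**The case against.** The best defence is that Appendix 5 supplements section 7.5. On that view, withholding at presentation does not exclude a later stop under 7.5.4, and a site that follows the stricter text breaks neither. Section 9.1 requires treatment to end for adverse events that call for discontinuation, and 7.5.4 also stops treatment whenever the investigator sees a substantial risk. An event that is life-threatening or needs hospital admission is a serious adverse event, reported within 24 hours and passed to the Chief Investigator. Unnoticed re-dosing is therefore less likely than the tables alone suggest.

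Much of this stands. The risk lies with sites that rely on the Appendix 5 row, and the safety reporting route lowers it. But the defence works only if the reader already knows that section 7.5 prevails, and the protocol does not say so. Nor is the endocrine row merely silent: by making the hold conditional on clinical need, it tells a site that dosing may go on where need is not found.

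The objection also limits the skin point. A reader might infer that Appendix 5 contradicts section 7.5 for every grade 4 skin toxicity. The documents do not support that. The table covers maculopapular rash only and refers the rest to the Investigator's Brochure, which is not at hand. For suspected SJS or TEN, section 7.5.2 and Appendix 5 both say hold.

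**Conclusion.** The endocrine contradiction is real at grades 3 and 4. A smaller mismatch exists for grade 4 maculopapular rash. No statement of precedence resolves either. The size is textual: three event-and-grade combinations, in the two of six tables that lack a permanent stop. With no event rates in the protocol, an expected number of patients would be a guess. The conclusion assumes that the events are drug-related and graded by CTCAE v5.0.

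Two wider inferences should be resisted. One is that the restart rule for grade 1 pneumonitis also conflicts, since 7.5.2 says "Drug-related pulmonary toxicity, diarrhoea or colitis must have resolved to baseline levels before treatment is resumed" and Appendix 5 says "May resume study treatment upon improvement or resolution". A grade 1 hold is optional in both texts, and a conflict appears only if the 7.5.2 line, which follows its delay rules, is extended to that optional hold. The other is that the inconsistency affects the response-rate analysis. It bears on who continues treatment; the primary analysis rule does not change.

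The correction is inexpensive and protects patients, so it should be made.

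**What to change.** 1. State in section 7.5.2 and at the head of Appendix 5 that section 7.5 governs where the two differ.
2. Split the endocrine row. Grade 3: delay until controlled on physiologic hormone replacement, in line with the restart line in 7.5.2. Grade 4: discontinue. If the sponsor wants patients with a controlled grade 4 endocrinopathy to continue, add a separate, explicit sentence to 7.5.4. The existing exceptions sub-bullet is the wrong place, because most of its entries are events below grade 4.
3. Leave the section 7.5.2 grade 2 rule unchanged and let the grade 2 endocrine row point to it.
4. Split the rash row so that grade 3 is withheld and grade 4 discontinued.
5. State in 7.5.4 whether suspected or confirmed SJS or TEN is a hold or a stop.

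The cost is a wording amendment and notice to sites, with no added procedures or patients. The downside is a few longer holds and, unless the sponsor adds the optional sentence, possible loss of treatment for a patient whose grade 4 endocrinopathy is controlled on hormones.
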